1.2 Secondary Objectives

Clinical:

1. To assess overall response rate (ORR) and overall survival (OS)
2. To assess time to treatment failure (TTF)

Pre-clinical/Exploratory:

1. To determine whether baseline AKT activation is predictive for clinical benefit after treatment with MK-2206 or everolimus.
2. To determine whether circulating cytokines and angiogenic factors predict for clinical benefit after treatment with MK-2206 or everolimus.
3. To assess impact of karyotype on outcome in patients treated with MK-2206 or everolimus.

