5.5 Duration of Therapy

In the absence of treatment delays due to adverse events, treatment may continue until one of the following criteria applies:

- Disease progression,
- Intercurrent illness that prevents further administration of treatment,
- Unacceptable adverse events(s),
- Patient decides to withdraw from the study, or
- General or specific changes in the patient's condition render the patient unacceptable for further treatment in the judgment of the investigator.
- Pregnancy

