| Grade 1 | CT scans with lung windows and pulmonary function testing including: spirometry, DLCO, and room air O ₂ saturation at rest. Repeat chest x-ray/CT scan every 2 Cycles until return to baseline. | No specific therapy is required | Administer 100% of everolimus dose. |
| Grade 2 | CT scan with lung windows and pulmonary function testing including: spirometry, DLCO, and room air O ₂ saturation at rest. Repeat each subsequent Cycle until return to baseline. Consider bronchoscopy * | Symptomatic only. Prescribe corticosteroids if cough is troublesome. | Hold everolimus dose until recovery to ≤ Grade 1. Restart everolimus at a reduced dose (only if patient recovers to Grade 1 within 3 weeks and only if the patient shows evidence of clinical benefit from the agent) Patients will be withdrawn from the study if they fail to recover to ≤ Grade 1 within 3 weeks. |
| Grade 3 | CT scan with lung windows and pulmonary function testing including: spirometry, DLCO, and room air O ₂ saturation at rest.; Repeat each subsequent Cycle until return to baseline. Bronchoscopy is recommended * | Prescribe corticosteroids if infective origin is ruled out. Taper as medically indicated. | Hold treatment until recovery to ≤ Grade 1. May restart protocol treatment within 3 weeks at a reduced dose (by one level) if evidence of clinical benefit. Patients will be withdrawn from the study if they fail to recover to ≤ Grade 1 within 3 weeks. |
| Grade 4 | CT scan with lung windows and required pulmonary function testing includes: spirometry, DLCO, and room air O ₂ saturation at rest. Repeat each subsequent Cycle until return to baseline. Bronchoscopy is recommended *. | Prescribe corticosteroids if infective origin is ruled out. Taper as medically indicated. | Discontinue treatment. |

*A bronchoscopy with biopsy and/or bronchoalveolar lavage is recommended.

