11.1.4.3 Evaluation of Best Overall Response

The best overall response is the best response recorded from the start of the treatment until disease progression/recurrence (taking as reference for progressive disease the smallest measurements recorded since the treatment started). The patient's best response assignment will depend on the achievement of both measurement and confirmation criteria.

For Patients with Measurable Disease (*i.e.*, Target Disease)

| Target Lesions | Non-Target Lesions | New Lesions | Overall Response | Best Overall Response when Confirmation is Required* |
|---|-----------------------------|-------------|------------------|--|
| CR | CR | No | CR | ≥4 wks. Confirmation** |
| CR | Non-CR/Non-PD | No | PR | ≥4 wks. Confirmation** |
| CR | Not evaluated | No | PR | |
| PR | Non-CR/Non-PD/not evaluated | No | PR | |
| SD | Non-CR/Non-PD/not evaluated | No | SD | documented at least once ≥4 wks. from baseline** |
| PD | Any | Yes or No | PD | no prior SD, PR or CR |
| Any | PD*** | Yes or No | PD | |
| Any | Any | Yes | PD | |
| 
* See RECIST 1.1 manuscript for further details on what is evidence of a new lesion.
 
** Only for non-randomized trials with response as primary endpoint.
 
*** In exceptional circumstances, unequivocal progression in non-target lesions may be accepted as disease progression.
 
Note: Patients with a global deterioration of health status requiring discontinuation of treatment without objective evidence of disease progression at that time should be reported as “symptomatic deterioration.” Every effort should be made to document the objective progression even after discontinuation of treatment.
 | | | | |

For Patients with Non-Measurable Disease (i.e., Non-Target Disease)

| Non-Target Lesions | New Lesions | Overall Response |
|--------------------|-------------|------------------|
| CR | No | CR |
| Non-CR/non-PD | No | Non-CR/non-PD* |
| Not all evaluated | No | not evaluated |
| Unequivocal PD | Yes or No | PD |
| Any | Yes | PD |

* 'Non-CR/non-PD' is preferred over 'stable disease' for non-target disease since SD is increasingly used as an endpoint for assessment of efficacy in some trials so to assign this category when no lesions can be measured is not advised

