13.4 Statistical Analysis Plan

The primary endpoint, progression-free survival (PFS), is defined as the time interval between date of treatment and date of disease progression, date of death or last follow-up date, whichever occurred first. The probability of PFS be estimated using the Kaplan-Meier method and will be compared between the two treatment arms using stratified log-rank test. Patients' safety data will be summarized by treatment arm, category, severity and relevance.

For secondary analyses, the Kaplan-Meier method will be used to estimate overall survival (OS) and time to failure (TTF), and stratified log-rank test will be used to compare between the two treatment arms. The OS is defined as the time interval between the date of treatment and the date of death or last follow-up, whichever occurred first. The TTF is defined as the time interval between the date of treatment and the date of disease progression, date of death, date of treatment discontinuation due to severe toxicity or last follow-up date, whichever occurred first. Overall response (OR) is defined as CR+PR and logistic regression model will be fit to assess the effect of treatment on the rate of OR.

Since the correlative studies being performed are by nature exploratory, and have not been

performed before in patients with RCC receiving mTOR inhibitors or AKT inhibitors, powering of these endpoints is not possible. Clinical benefit is defined as CR+PR+SD and again, we will fit logistic regression models to assess the effects of treatment, AKT activation, circulating cytokines and angiogenic factors, and karyotype on clinical benefit. The interaction effect between treatment and these exploratory factors will also be evaluated.

For virtual karyotyping, technique specific statistical analyses are outlined in [Appendix G](#).

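### TTF counts only progression, death and severe-toxicity stops, so patients taken off drug for other failure reasons stay failure-free after treatment ends

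*Combined protocol and SAP*

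**What the plan says.** Section 1.2 makes TTF a secondary clinical objective and calls it time to *treatment* failure; Section 13.1 shortens this to time to failure. Section 13.4 runs the clock from the start of treatment to the earliest of "date of disease progression, date of death, date of treatment discontinuation due to severe toxicity or last follow-up date". It compares the arms by Kaplan-Meier and a stratified log-rank test. PFS, in the same section, has the same start and the same end dates except for the severe-toxicity stop.

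Section 5.5 gives six grounds for ending treatment. Besides progression and unacceptable adverse events (no grade stated), they include "Intercurrent illness that prevents further administration of treatment", patient withdrawal, changes in condition that "render the patient unacceptable for further treatment in the judgment of the investigator", and pregnancy.

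Two everolimus rules in Section 6.2 also end treatment without requiring a severe event. The grade 2 pneumonitis row of Table 5 says "Patients will be withdrawn from the study if they fail to recover to ≤ Grade 1 within 3 weeks". The last row of Table 4 stops the drug after any toxicity that has needed an interruption of at least 4 weeks.

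The note to the response table in 11.1.4.3 gives a separate category, symptomatic deterioration, to "Patients with a global deterioration of health status requiring discontinuation of treatment without objective evidence of disease progression".

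**The concern.** An endpoint with this name should record when the assigned treatment stopped working or could no longer be given. Under 13.4 as written, a patient who stops because of decline without a qualifying scan, or because a grade 2 toxicity would not resolve, has not failed. The clock keeps running off drug until progression or death is recorded, or the patient is censored at last contact.

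Two things are at stake. First, TTF would overstate time on successful treatment, and would add only severe-toxicity stops to what PFS already shows. Second, censoring a patient who stopped because of deterioration is plausibly informative: that patient is likely to be closer to progression or death than those still at risk.

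**Working it through.** The plan gives no event count, power or expected value for TTF, so there is no figure to reproduce. The check sets the definition beside each way treatment can end.

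| Why treatment ends | Where | TTF event under 13.4? |
|---|---|---|
| Progression | 5.5 | Yes |
| Death | 13.4 | Yes |
| Severe toxicity | 5.5, Section 6 | Yes |
| Toxicity that is not severe | 5.5; Table 5, grade 2 row; Table 4, last row | No |
| Symptomatic deterioration | 11.1.4.3 | No |
| Intercurrent illness | 5.5 | No |
| Investigator-judged change in condition | 5.5 | No |
| Withdrawal, pregnancy | 5.5 | No |

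**What *severe* means.** Section 13.4 does not define it. Elsewhere, 2.3.4 uses it for grade 3 stomatitis, 2.3.5 describes grades 1 and 2 as mild to moderate, and the safety rule in 13.1 uses grade 3 or higher with a treatment stop. The fourth row rests on that reading; the rows below it do not.

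**Whether another section repairs it.**
- The treatment-failure convention in 13.5.2 governs the response rate, not TTF.
- Section 5.2 requires imaging and a response assessment once treatment ends for any reason, and 11.1.4.3 asks that objective progression still be sought after a stop for deterioration. Some omitted stops will become events this way. A toxicity or illness stop with no progression on that scan will not.
- Under 5.7, meeting any 5.5 criterion removes the patient from study. Section 5.6 then follows patients every 3 months, possibly by remote contact or chart review, with no imaging schedule, and ends follow-up of an arm once its median OS is reached. Later progression can be dated late or missed.

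**Illustration of size.** None of the following assumptions comes from the documents, apart from the design medians.
- m is the median TTF as written. The Section 13.2 PFS medians stand in for it: 4.9 months (everolimus) and 8.2 months (MK-2206). This supposes no severe-toxicity stops.
- Times are exponential, and omitted stops are independent of progression and death.
- q is the share of all treatment endings that 13.4 omits, varied from 5% to 30%.

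The rate as written is ln 2 / m. With omitted stops counted it becomes (ln 2 / m) / (1 − q), so the median becomes m(1 − q).

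| q | Everolimus median (months) | MK-2206 median (months) |
|---|---|---|
| 0 (as written) | 4.90 | 8.20 |
| 5% | 4.66 | 7.79 |
| 10% | 4.41 | 7.38 |
| 20% | 3.92 | 6.56 |
| 30% | 3.43 | 5.74 |

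The hazard ratio (MK-2206 to everolimus) is (4.9/8.2) × (1 − q for everolimus)/(1 − q for MK-2206):
- equal shares: 0.598, unchanged;
- everolimus 10%, MK-2206 20%: 0.598 × 0.90/0.80 = 0.67;
- everolimus 20%, MK-2206 10%: 0.598 × 0.80/0.90 = 0.53;
- extremes within 5% to 30%: 0.598 × 0.70/0.95 = 0.44 and 0.598 × 0.95/0.70 = 0.81.

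**The case against.** The rule in 13.4 is complete and computable, and a narrow TTF can be defended. Intercurrent illness, withdrawal and pregnancy are not obviously failures of a drug, and in an open-label trial (13.1) discretionary stops are open to preference. TTF is secondary and unpowered. These points stand as reasons to keep the narrow version as a sensitivity analysis and to leave withdrawal and pregnancy as an explicit choice. They do not explain leaving out unresolved toxicity and symptomatic deterioration, which the protocol itself recognises as grounds for stopping.

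The illustration is generous. Independence gives a patient stopped for global deterioration the same remaining time to progression or death as anyone else, which overstates the error in that group. Using PFS medians also supposes no severe-toxicity stops, whereas 13.1 monitors exactly those against a 30% rate.

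Three stronger readings are tempting, and the documents do not support them.
- *A reader might infer that TTF nearly duplicates PFS.* How close they are depends on the number of severe-toxicity stops, which is unknown. What can be said is that such stops are the only difference.
- *A reader might infer that the omission biases the comparison between arms.* Table 5 and the last row of Table 4 apply to everolimus. Section 6.1 has its own four-week limit for MK-2206, though it follows the grade 3 text, and it manages persistent grade 2 rash by holding and restarting. Unequal shares are possible, but no document gives them.
- *A reader might infer that grade 2 stops are certainly excluded.* The word *severe* is undefined, and Section 5.4 lists grade 2 everolimus pneumonitis as dose-limiting. The documents' usual wording favours grade 3, but the definition has to settle it.

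**Conclusion.** The point holds for a secondary endpoint and should be corrected. Applied exactly, 13.4 gives a TTF that departs from the objective in 1.2: patients permanently off drug for non-severe toxicity, symptomatic deterioration, intercurrent illness or investigator judgment are failure-free until a later event, or are censored, and no other section closes the gap. The toxicity part rests on reading *severe* as grade 3 or higher; the rest does not.

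The true size is unknown. Under the stated model the median shortens by the omitted share itself, and the hazard ratio changes only if shares differ by arm. The 0.44 to 0.81 range shows sensitivity to chosen values and is not evidence of bias. The end-of-treatment scan will reduce the effect. PFS, its sample size and the stopping rules are unaffected.

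**What to change.** In 13.4, define the TTF event as the earliest of:
- documented progression, at its own date;
- death from any cause;
- permanent discontinuation of study drug for toxicity of any grade, symptomatic deterioration, intercurrent illness or investigator judgment, dated at the recorded decision to stop or removal.

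Do not date every event at last dose. That would move many progressions back to the preceding dose, by intervals that differ between a weekly and a daily drug, and after a long hold it would place the event well before the decision to stop.

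State whether withdrawal and pregnancy are events or censored, with a sensitivity analysis that treats them the other way. Keep the present narrow definition as a further sensitivity analysis, with *severe* defined by grade.

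The cost is a few sentences in 13.4 and no new data collection. Section 5.7 already requires the reason and date of removal, and the Appendix K schedule lists last dose date, off-treatment reason and off-protocol date. The reason coding must separate symptomatic deterioration from other stops; the documents do not show the code list. The downside is a somewhat shorter TTF that includes some discretionary stops in an open-label trial.

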13.2 Sample Size/ Power Calculation

Assuming that the median progression-free survival (PFS) is 4.9 months and 8.2 months for the everolimus and MK2206 arm, respectively and patients will be randomized with 2:1 ratio into the MK2206 arm and the everolimus arm, then with a total of 75 events (i.e., disease progression or death), we will have an 80% power to detect such a 67% increase in median PFS using one-sided log-rank test and at a 0.10 significance level. The total number of patients to be enrolled will be 105, with 35 on the everolimus arm and 70 on the MK2206 arm. The above calculation also assumes an accrual rate of 4 patients per month, thus it will take 26.3 months to accrue all 105 patients. The maximum study duration will be around 29 months, which include patients' accrual period and a follow-up period. East5 software was used for the sample size/power calculation.

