Arrays created as outlined in will be stained with antibodies against the following proteins and others that may be deemed clinically relevant: Total AKT, AKT^{S473}, AKT^{T308}, p70 S6K, S6, phospho S6, p27, NFkB, mTOR, phospho mTOR. RCC-specific antibody optimization has already been performed by our lab.

6. Sample Analysis

Once staining has been performed, sample quantitation will be performed using an Ariol Image analysis system. Areas of viable tumor will be gated, and necrotic and nonviable regions masked. Acquisition characteristics will be set by the PI and the core facility staff. Percentage involvement of core by stain of interest will be captured as a continuous variable. Averaging of triplicate samples will be performed for each case. In the situation where significant outliers exist, scanning quality will be assessed and samples discarded if variability is due to low sample quality.

7. Statistical Analysis

Statistical Analysis will be performed according to guidelines in [Section 13.4](#) of the protocol.

**APPENDIX I CYTOKINE AND ANGIOGENESIS FACTOR ANALYSIS:
 [name], COLLABORATOR**

1. Collection of Specimen(s)

Venous blood will be collected for Cytokine and Angiogenic factors as outlined below.

Collect blood into 1x 10ml EDTA vacutainer (BD# 366457), 1 x 10ml SST vacutainer (BD# 367985), and 2 x 8ml Sodium Citrate CPT vacutainers (BD# 362761) following institutional procedures. All samples should be clearly labeled with the NCI Protocol Number, Subject Number, Specimen, and Timepoint using an indelible marker. A detailed laboratory manual will be provided.

2. Handling of Specimens(s)

Serum and EDTA treated Plasma Samples:

Allow the SST vacutainer to clot for approximately 20 minutes at room temperature prior to centrifugation. Centrifuge the SST and EDTA vacutainers at 1200xg for 20 minutes at 4°C. Remove the serum and plasma layers, respectively, and transfer to cryovials. Freeze serum and plasma samples at or below -80°C until shipment.

Sodium Citrated Plasma and Peripheral Blood Mononuclear Cell Layer (PBMC)

Samples:

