MIP-1 β
Eotaxin
CTACK
GRO-A
MCP-3
MIF
MIG
TRAIL

Other interleukins

IL-1ra
IL-2
sIL-2RA
IL-3
IL-4
IL-5
IL-7
IL-9
IL-10
IL-13
IL-16
IL-17
IL-18

Growth factors

GM-CSF
G-CSF
M-CSF
SCF
NGF-B

Statistical Analysis:

We have investigated potential blood-based biomarkers in a randomized phase II trial of sorafenib vs. sorafenib and interferon. Using multiplexed bead assays (MBAs) and ELISAs to broadly assess a profile of cytokines and angiogenic factor (CAFs), we have identified plasma markers that predicted improved progression-free survival (PFS) in patients in each arm. A CAF signature, derived by combining individual markers, was more predictive than individual markers alone. *In vitro* studies and patient data suggest that CAFs may be regulated by tumor hypoxia, Akt/mTOR signaling, and other pathways. Based on this and additional studies in other cancer types, we *hypothesize that broad profiling of CAFs in plasma of RCC patients can be used to identify groups of patients that receive different degrees of benefit from different therapeutic regimen*. We also hypothesize that CAF profiling can identify markers of therapeutic resistance and tumor pathway activation. Our primary goal in this project is to develop predictive biomarkers of benefit (prolongation in PFS and overall survival, OS) using plasma specimens from this randomized phase II trial.

For the multiplexed bead arrays, the data is assessed in the following manner. For each plate, the standard curves are assessed to ensure that the expected assay range was achieved. For each individual sample, the mean concentration is calculated for duplicate samples, and the coefficient of variance % (CV%) is calculated for all analytes. If the median CV% was greater than 25%, analysis of the sample is repeated. In the rare case that the repeat CV% was greater than 25%, one of the two analyses is selected based on lower CV% and consistency with prior values.

The multiplexed beads are assessed in a similar manner. For each plate, the standard curves are assessed to ensure that the expected assay range was achieved. For each individual sample, the mean concentration is calculated for duplicate samples, and the CV% is calculated. If the CV% for an individual sample is greater than 50%, the value is rejected.

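### The AKT biomarker question is planned only as a logistic model on CR+PR+SD, which uses about a quarter of the PFS events and gives the treatment-by-AKT test much less power than a PFS model on the same patients

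*Combined protocol and SAP*

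**What the plan says.** Section 13.4 states "Clinical benefit is defined as CR+PR+SD and again, we will fit logistic regression models" to assess treatment, AKT activation, circulating factors and karyotype. It adds that interactions between treatment and these factors will be evaluated. It calls the correlative studies exploratory and says they cannot be powered.

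The appendices differ by marker:

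- **AKT (Appendix H, item 7):** "Statistical Analysis will be performed according to guidelines in" Section 13.4. No other model is given.
- **Karyotype (Appendix G, item 6):** univariate and multivariate Cox regression on PFS and OS. Section 13.4 itself points to this appendix.
- **Circulating factors, CAF (Appendix I):** the goal is to "develop predictive biomarkers of benefit (prolongation in PFS and overall survival, OS", and Cox models are planned for marker changes and for combined markers.

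On the outcome, Section 11.1.4.1 defines SD without a minimum duration. The four-week condition in the Section 11.1.4.3 table carries a footnote limiting it to non-randomized trials with response as primary endpoint, so it does not apply here. Section 11.1 sets re-evaluation every eight weeks.

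Section 1.2 lists AKT first among the exploratory objectives. Section 2.5 states two AKT hypotheses: one about response to MK-2206, the other about PFS on everolimus.

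**The concern.** If SD of any duration counts, a patient who progresses at four months and one who progresses at two years both count as benefiting. The binary outcome separates only those who fail by about the first scan from everyone else. A treatment-by-marker interaction is hard to detect even with full follow-up, so dropping most of the outcome information matters more here than for a main effect.

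AKT is the marker tied to the trial's rationale in Section 2.4, yet it is the one marker with no time-to-event analysis. One of its two hypotheses is stated in PFS terms, and the planned model does not address it. At stake is whether a null AKT interaction would say anything about the biology. The primary PFS comparison is not affected.

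**Working it through.** **Inputs from Section 13.2.** "median progression-free survival (PFS) is 4.9 months and 8.2 months for the everolimus and MK2206 arm"; "with a total of 75 events (i.e., disease progression or death), we will have an 80% power"; "105, with 35 on the everolimus arm and 70 on the MK2206 arm"; "accrual rate of 4 patients per month, thus it will take 26.3 months to accrue all 105 patients"; study duration about 29 months.

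**Assumptions not in the documents.** Exponential PFS, marker prevalence 50%, no marker effect on everolimus, a binary marker, and the effect sizes and evaluable shares shown.

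**1. The plan's own figure.** HR = 4.9/8.2 = 0.598, ln HR = −0.515. With 2:1 allocation and 75 events, z = √(75 × 2/9) × 0.515 = 2.10. At one-sided 0.10 power is Φ(2.10 − 1.28) = 79%, which agrees with the stated 80%.

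**2. What CR+PR+SD measures.** Eight weeks is 56/30.44 = 1.84 months. The proportion progression-free is exp(−ln 2 × 1.84/median):

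- everolimus: exp(−0.693 × 1.84/4.9) = 77.1%, so 35 × 0.229 = 8.0 failures
- MK-2206: exp(−0.693 × 1.84/8.2) = 85.6%, so 70 × 0.144 = 10.1 failures

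The total is about 18 failures, and 18.1/75 = 24% of the planned PFS events.

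**3. Interaction power by formula.** Power = Φ(|δ|/SE − z), where z is 1.96 (two-sided 0.05) or 1.28 (one-sided 0.10). There are four treatment-by-marker cells of 17.5, 17.5, 35 and 35 patients. For logistic regression, SE = √Σ 1/(n·p·(1−p)). For Cox, SE = √Σ 1/events, with expected events from uniform accrual over 105/4 = 26.25 months and analysis at 29 months.

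Take MK-2206 HR 0.35 in marker-positive and 1.0 in marker-negative patients. The geometric mean is √0.35 = 0.59, close to the design HR, so this amounts to placing the whole design effect in the marker-positive half.

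- Logistic: p = 0.771, 0.771, 0.771 and 0.913 (marker-positive on MK-2206). n·p·(1−p) = 3.09, 3.09, 6.18 and 2.78, so SE = 1.08. δ = 1.14, and |δ|/SE = 1.05. Power is Φ(1.05 − 1.96) = 18%, or 41% at one-sided 0.10.
- Cox: events 14.4, 14.4, 28.8 and 17.9, so SE = 0.479. δ = ln 0.35 = −1.05, and |δ|/SE = 2.19. Power is Φ(2.19 − 1.96) = 59%, or 82% at one-sided 0.10.

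The same formulas over a range of effects, centred on the design HR:

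| Ratio of HRs | Evaluable | Logistic vs Cox, two-sided 0.05 | Logistic vs Cox, one-sided 0.10 |
|---|---|---|---|
| 0.5 | 100% | 11% vs 31% | 28% vs 57% |
| 0.33 | 100% | 20% vs 64% | 43% vs 85% |
| 0.25 | 100% | 28% vs 82% | 54% vs 94% |
| 0.5 | 50% | 7% vs 18% | 22% vs 40% |
| 0.25 | 50% | 16% vs 53% | 38% vs 77% |

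**4. Simulation check.** The logistic formula is optimistic when cells are sparse: in step 3 only about 35 × 0.087 = 3 failures are expected among marker-positive MK-2206 patients. Simulated trials (600 to 2,000 per setting, all 105 evaluable) gave:

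- HR 0.35 vs 1.0: logistic Wald 11–13% against Cox 55–59% at two-sided 0.05, and 33–36% against 77–81% at one-sided 0.10. The logistic interaction could not be estimated in about 7–8% of trials.
- The same logistic model with a likelihood-ratio test: about 21% at two-sided 0.05. Its rejection rate under the null is about 6–8%, so part of that gain is not real.
- Ratio of HRs 0.5: logistic about 6–7% (Wald) or 12–13% (likelihood ratio) against Cox 28–33%, at two-sided 0.05.

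**The case against.** The strongest reply is that the plan discloses the limitation: these analyses are labelled exploratory and unpowered, and low interaction power in a 105-patient phase 2 trial is expected. That stands as a reason not to call this a design error. It explains why no sample size was set, but not why an outcome with a quarter of the available events should be the only one for AKT.

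Second, the logistic model fits the wording of the objective, which asks about clinical benefit, and the MK-2206 hypothesis, which is about response. That also stands, and is why the model should be kept. It does not cover the everolimus hypothesis, which is about PFS.

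Third, the size depends on choices the documents do not make. No test level is set for biomarkers, the Wald test is not specified, and prevalence and effect size are assumed. Appendix H captures staining as a continuous variable, which a half-and-half binary marker only approximates. The count of 18 could also rise, because Section 13.5.2 treats unknown response as failure. These points move the figures, but in every setting examined Cox has the higher power.

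A reader might infer that all the biomarker work throws away PFS. The documents do not support that: Appendices G and I plan Cox models for karyotype and CAF. What they lack is a named treatment-by-marker term, so the only interaction test actually written down, for any marker, is the logistic one in 13.4.

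**Conclusion.** The point holds for AKT. Its only planned model uses an outcome with about 18 failures in place of 75 PFS events, and its interaction power is well below that of a Cox PFS model on the same patients: roughly one fifth of it at two-sided 0.05, and under half at one-sided 0.10, for HR 0.35 vs 1.0 with a Wald test. A likelihood-ratio test narrows the gap without closing it. For karyotype and CAF the point reduces to a missing interaction term and a mismatch between 13.4 and the appendices.

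Two stronger readings should be resisted. That the logistic test has almost no power is fair only for a moderate interaction or for the Wald test at two-sided 0.05; at the trial's one-sided 0.10 level the range is about 22% to 54% by formula. That Cox would settle the AKT question is not supported either: at a ratio of HRs of 0.5 it reaches only about 30% at two-sided 0.05 with everyone evaluable, and 18% with half evaluable. Tissue collection is optional, so the evaluable number may well be below 105.

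The 24% event share rests on exponential PFS at the design medians. The power figures rest also on the assumed marker inputs.

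**What to change.** In Section 13.4 and Appendix H, make the main AKT analysis a Cox model for PFS with treatment, the AKT marker as the continuous variable already captured, and their interaction. Name the same interaction term in the Cox models for karyotype (Appendix G) and CAF (Appendix I), so that 13.4 and the appendices agree on the model and on what clinical benefit means.

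Keep the logistic CR+PR+SD model as a supporting analysis and say how long SD must last to count. A longer duration alone is not a substitute: with a 24-week requirement, logistic power by the same formula is 18% and 37% at ratios of HRs of 0.5 and 0.33, against 31% and 64% for Cox (two-sided 0.05, all evaluable). Continue to label all of this exploratory.

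The cost is wording only. PFS is already the primary endpoint, and Cox models are already planned for the other markers. No further patients, samples or visits are needed.
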